### **4.7. Protocol Deviations**

Protocol deviations and major protocol deviations will be identified and documented based on a review of protocol deviations before database lock and treatment unblinding and will be used to define the Evaluable Population. The categories of major protocol deviations to be reviewed include, but are not limited to, participants who:

- Did not meet key inclusion/exclusion criteria in the judgement of the evaluability committee.
- Received disallowed concomitant medication that could meaningfully impact results.
- Had overall treatment compliance rate <80% or >120% (including Single-blind Run-in Period and Double-blind Treatment Period).

This document is confidential.

In addition, the sub-categories 'Related to COVID-19' and 'Unrelated to COVID-19' will be collected to assess the impact of COVID-19 on the protocol deviation data.

The number and percentage of participants with major protocol deviations will be summarized by type of deviation and relationship to COVID-19 and by treatment arm for the ITT Population. All protocol deviations will be presented in a data listing.

This document is confidential.

## 5. General Aspects for Statistical Analysis

### 5.1. General Methods

All applicable data will be summarized by randomized treatment arm, unless specified otherwise. For summary tables, unless otherwise noted, participants who were randomized to placebo will be summarized as:

- 1) PBO1: participants who were randomized to placebo under Protocol Amendment 3 or earlier,
- 2) PBO2: participants who were randomized to placebo under Protocol Amendment 4 or later, and
- 3) Overall: participants who were randomized to placebo under any version of the protocol.

The participants who were randomized to olinciguat dosing regimens will be summarized as:

- 1) 2 mg: participants who were randomized to 2 mg olinciguat dosing regimen under Protocol Amendment 3 or earlier,
- 2) 4 mg: participants who were randomized to 4 mg olinciguat dosing regimen under Protocol Amendment 3 or earlier,
- 3) 6 mg: participants who were randomized to 6 mg olinciguat dosing regimen under Protocol Amendment 3 or earlier, and
- 4) 18 mg: participants who were randomized to 18 mg olinciguat dosing regimen under Protocol Amendment 4 or later

For safety analysis, the data will be summarized by treatment arm actually received.

In addition, data will be summarized by scheduled visit and/or time-point where appropriate. Unscheduled or repeat assessments will not be included in summary tables, but will be included in listings.

Continuous variables will be summarized using descriptive statistics, including the number of observations (n), mean, standard deviation (SD), median, minimum, maximum and interquartile range (IQR). Categorical variables will be summarized using frequencies and percentages. Unless otherwise specified, percentages will be based on the total number of non-missing values.

Unless otherwise specified, all confidence intervals (CIs) will be 2-sided with a confidence level of 95%. No adjustments will be made for multiplicity.

All statistical analyses will be performed using SAS Version 9.4 or later for Windows.

### 5.2. Key Definitions

#### 5.2.1. Baseline

Unless other stated, baseline is defined as the last non-missing value measured before administration of randomized study drug on Day 1 of the Treatment Period.

#### 5.2.2. Change from Baseline

Change from baseline will be calculated for the post-baseline assessment as:

$$\text{Change from baseline} = \text{post-baseline value} - \text{baseline value}$$

This document is confidential.

### 5.2.3. Study Day

"Study Day" represents the number of days relative to initiation of randomized study drug administration in the Treatment Period (ie, Day 1). If the assessment date is after the date of Day 1, the study day is calculated as (date of assessment - date of Day 1 + 1). If the assessment date is prior to the date of Day 1, the study day is calculated as (date of assessment – date of Day 1). There is no study day of 0.

### 5.2.4. TEAE, SAE, On-therapy SAE

TEAEs are defined as AEs with a reported started date/time that is on/after the first dose date/time the participant receives randomized treatment through 7 days after the last dose of study medication.

SAEs are AEs that result in death, are life-threatening, require hospitalization or prolongation of existing hospitalization, are persistent or result in significant disability/incapacity, result in a congenital anomaly/birth defect, or are important medical events (eg, events that may not result in death, are life threatening, or require hospitalization; such events may be considered serious when, based on appropriate medical judgment, it may jeopardize the participant and may require medical or surgical intervention to prevent 1 of the outcomes listed in the wider SAE definition).

On-therapy SAEs are those SAEs that start after the participant has received the first dose of randomized study drug and through 28 days after the final study drug dose.

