3.8.8.1 Definition of Adverse Event

An AE is any untoward medical occurrence in a patient or clinical investigation subject administered a pharmaceutical product and which does not necessarily have to have a causal relationship with this treatment.

An AE, therefore, can be any unfavorable and unintended sign (including an abnormal laboratory finding, for example), symptom, or disease temporally associated with the use of a medicinal product, whether or not considered related to the medicinal product.

An AE includes, but is not limited to, the following:

- Any unfavorable changes in general condition
- Any clinically significant worsening of a preexisting condition
- Any intercurrent diseases and accidents

Note: A procedure is not an AE, but the reason for a procedure may be an AE.

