3.8.8.7 Recording Adverse Events

AEs will be collected and recorded from the time the patient signs the ICF at the Screening Visit through the last Follow-up Visit. All AEs, regardless of the assumption of a causal relationship with study procedures or study medication, must be recorded in the patient's source documentation and subsequently on the appropriate AE page of the patient's eCRF. This record includes AEs the patient reports spontaneously, those observed by the Investigator, and those elicited by the Investigator in response to open-ended questions during the study, such as "Have you had any health problems since your last visit?"

For every AE, the Investigator must:

- Provide an assessment of the severity, causal relationship to the study medication, and seriousness of the event
- Document all actions taken with regard to the study medication (eg, no action taken, treatment interrupted, or treatment discontinued)
- Detail any other treatment measures taken for the AE, including concomitant medications and/or procedures

Laboratory abnormalities and changes in vital signs, physical examination findings, and 12-lead ECG parameters should be considered AEs and reported on the AE page of the patient's eCRF if the Investigator considers them clinically significant and are not already associated with an AE.

Any medical condition that is present when a patient is screened and does not worsen in severity and/or frequency should be reported as Medical History and not as an AE. However, if the condition worsens to a clinically significant degree at any time during the study, it should be reported as an AE.

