4. STUDY ENDPOINTS

4.1 PRIMARY ENDPOINTS

4.1.1 Safety

- Incidence, frequency, and severity of TEAEs and study drug-related TEAEs in IW-1701-treated patients compared with placebo-treated patients over the study

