### 3. Study Objectives

#### 3.1. Study Objectives and Endpoints

Table 1 provides the study objectives and the corresponding endpoint(s) that will be summarized and analyzed to determine if the objective is met.

Table 1: Study objectives and corresponding endpoints

Objective	Endpoint
	Primary
The primary objective is to assess the safety and tolerability of oral, once-daily (QD) olinciguat when administered for approximately 12 weeks to participants aged 16 to 70 years with sickle cell disease (SCD).	Incidence (number and percentage of patients) and frequency (number of events) of treatment-emergent adverse events (TEAEs) Incidence of TEAEs by severity Incidence of study drug-related TEAEs
Exploratory Patient-reported Outcomes	
To evaluate the effect of oral, once-daily olinciguat on symptoms of SCD, health-related quality of life, and biomarkers when administered for approximately 12 weeks to participants aged 16 to 70 years with SCD	Change from baseline in Sickle Cell Disease – Symptom Assessment Form (SCD-SAF) total score at Weeks 4, 8, 12, and End of Treatment (EOT) Pain as measured on the 11-point numerical rating scale (NRS) by week and for the overall Treatment Period Percent change from baseline in pain as measured on the 11-point NRS by week and for the overall Treatment Period Change from baseline in pain as measured on the 11-point NRS by week and for the overall Treatment Period Change from baseline in fatigue as measured on the 11-point NRS by week and for the overall Treatment Period Change from baseline ASCQ-Me pain impact score
Exploratory Pharmacodynamics	
To evaluate the effect of oral, once-daily olinciguat on symptoms of SCD, health-related quality of life, and biomarkers when administered for approximately 12 weeks to participants aged 16 to 70 years with SCD	Change from baseline in hemoglobin at Weeks 4, 8 and 12 Proportion of patients with change from baseline in hemoglobin $\geq 1$ g/dL at end of treatment Change from baseline in fetal hemoglobin at Weeks 4, 8 and 12
Exploratory Pharmacokinetics	
To evaluate the pharmacokinetics (PK) of oral, once-daily olinciguat when administered for approximately 12 weeks to participants aged 16 to 70 with SCD	Plasma concentrations of olinciguat at assessed timepoints

Note: Bolded parameters associate directly with corresponding endpoint(s).

This document is confidential.

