### 7.2. Adverse Events

AEs will be coded using the MedDRA Version 20.0 or later and will be classified by MedDRA SOC and PT.

AEs are collected from date of signed informed consent form (ICF) through the last Follow-up Visit. TEAEs, SAEs, and on-therapy SAEs are defined in [Section 5.2.4](#). Pre-treatment AEs during Screening are defined as AEs started on/after Screening Visit and before the first dose of Run-in placebo. Pre-treatment AEs during Single-blind Run-in Period are defined as AEs started on/after the first dose of Run-in placebo and before the first dose of randomized study drug.

The number and percentage of participants who experience at least 1 TEAE as well as those who experience each specific SOC and PT will be presented by treatment group for the Safety Population. For presentation of AE incidence, AEs will be sorted by SOC, and within each SOC, by PT in the decreasing incidence of the last column of summary table, and then the column before it one by one. AEs will also be presented by severity (CTCAE v.4.03; Grade 1–Grade 5). For AEs that change severity ratings, the AE will be included only once in the summaries, under the maximum severity rating assigned by the Investigator. Additionally, TEAEs and SAEs occurring in the first, second, and fifth week of the double-

This document is confidential.

blind Treatment Period will be listed separately to distinguish among any effects of the initial dose (Week 1), the up-titrated dose (Week 2), and the further up-titrated dose (Week 5).

AEs occurring during Screening and the Single-blind Run-in Period will be summarized and listed separately.

More specifically, the following summary tables will be provided:

1. Overall Summary of TEAEs
2. Incidence of TEAEs by SOC and PT
3. Incidence of TEAEs by SOC, PT, and severity
4. Incidence of TEAEs by SOC, PT and relationship to double-blind study drug
5. Incidence of on-therapy SAEs by PT
6. Incidence of AEs leading to study drug discontinuation by PT
7. Incidence of pre-treatment AEs during Screening by SOC and PT (Screened Population)
8. Incidence of pre-treatment AEs during Single-blind Run-in Period by SOC and PT (Single-blind Run-in Population)
9. Incidence of adverse events of special interest (AESIs) by PT
10. Incidence of TEAEs by SOC, PT, and region (US vs. Lebanon)
11. Incidence of VOCs by PT
12. Summary of VOC events by location (eg, extremity) and outcome (eg, acute chest syndrome)

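### SAP 5.2.4 has no worsening clause: an AE dated before randomized dosing that worsens on treatment stays out of the primary TEAE tables unless the site opens a new record

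*SAP*

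**What the plan says.** - **Primary endpoint.** Protocol 4.1.1 gives it as "Incidence, frequency, and severity of TEAEs and study drug-related TEAEs in IW-1701-treated patients compared with placebo-treated patients over the study". The protocol uses the term TEAE without defining it. SAP Table 1 carries the same endpoint as TEAE incidence and event count, incidence by severity, and incidence of drug-related TEAEs.
- **Definition.** The only definition is in SAP 5.2.4: "TEAEs are defined as AEs with a reported started date/time that is on/after the first dose date/time the participant receives randomized treatment". The window ends one week after dosing stops. On-therapy SAEs, in the same section, are SAEs that start after the first randomized dose and up to 28 days after the last dose.
- **Earlier events.** SAP 7.2 uses the same test: "Pre-treatment AEs during Single-blind Run-in Period are defined as AEs started on/after the first dose of Run-in placebo", up to the first randomized dose. Screening AEs are handled in the same way.
- **Changing grade.** SAP 7.2: "For AEs that change severity ratings, the AE will be included only once in the summaries, under the maximum severity rating".
- **Collection.** Protocol 3.8.8.7: "AEs will be collected and recorded from the time the patient signs the ICF at the Screening Visit through the last Follow-up Visit". Screening can last up to 43 days and includes 14 to 17 days of placebo run-in (Protocol 3.1).
- **Worsening as an AE.** Protocol 3.8.8.1 includes among AEs "Any clinically significant worsening of a preexisting condition". Protocol 3.8.8.7 says that a condition already present at screening is medical history, and becomes a reportable AE if it worsens to a clinically significant degree.

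**The concern.** The plan collects AEs for several weeks before randomized dosing, so some will be open on Day 1. Whether such an event then gets worse on olinciguat or placebo is a tolerability question, and tolerability is the primary objective. A rule that looks only at the start date cannot see it. The severity table is the most exposed: an event recorded at Grade 1 in run-in that reaches Grade 3 on treatment would not appear there at all. The separate listings for the first, second and fifth weeks, meant to distinguish the effects of the initial dose and the two up-titrations, draw on the same TEAE set and share the gap.

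**Working it through.** The SAP gives no figure to reproduce. The check is to follow one event through the rules and then see what a single omission is worth.

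**Tracing the event.** Take an AE with a fully known start date in the placebo run-in, Grade 1, still open at the first randomized dose, later Grade 3, and kept as one record.

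1. SAP 5.2.4: the start precedes the first randomized dose, so it is not a TEAE. The later grade is not consulted.
2. SAP 7.2: it is a run-in pre-treatment AE. The rule on changing severity shows that the plan expects one record to span a grade change. Nothing moves the start date to the time of worsening.
3. Output: it is absent from the SAP 7.2 tables of TEAEs by SOC and PT, by severity and by relationship, and from the severe and drug-related TEAE listings. The dedicated table that takes it is the run-in table, which shows SOC and PT without severity.
4. If it became serious on treatment, it also leaves the on-therapy SAE table if start there means AE onset. If start means the date it became serious, it stays in. The SAP does not say which.

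**How the result depends on the record.**

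| What the database holds | Rule | Result |
|---|---|---|
| Full pre-dose start date, one record, worsens on treatment | SAP 5.2.4, 7.2 | Pre-treatment |
| Start known only to the month or year of first randomized dose | SAP 5.3 imputes the first-dose date | TEAE |
| Start missing, not stopped before first randomized dose | SAP 5.3 | TEAE |
| Worsening entered as a new AE dated at the worsening | SAP 5.2.4 | TEAE |
| Condition present at screening, worsening reported as an AE with an on-treatment start date | Protocol 3.8.8.7, SAP 5.2.4 | TEAE |

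The first row is the gap. An AE with a vague start date is treated conservatively, while a well-dated AE that worsened on treatment is excluded.

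**Scale of one omission.** Planned sizes come from SAP 3.4 and 3.5.

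- 18 mg: 48 × 3/4 = 36; placebo under Amendment 4 and later (PBO2): 48 × 1/4 = 12.
- Each arm under Amendment 3 or earlier: 40 / 4 = 10.
- A patient whose only event is the omitted one lowers TEAE incidence by 1/36 = 2.8 points, 1/12 = 8.3 points or 1/10 = 10 points respectively.

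**Direction.** Observed difference = difference with these events counted − (omitted proportion on drug − omitted proportion on placebo). It is understated only if the omitted proportion is larger on drug. One omission in PBO2 is balanced by three at 18 mg, since 3/36 = 1/12 = 8.3 points.

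**The case against.** The strongest reply is that the protocol already treats worsening as an AE. Protocol 3.8.8.1 does so in general terms, and 3.8.8.7 requires it for conditions present at screening, which would cover many patients with chronic headache, dizziness or pain. An AE reported that way can carry an on-treatment start date and be a TEAE. This stands, and it narrows the gap. It does not close it: the 3.8.8.7 instruction concerns medical-history conditions, and neither document clearly tells the site to open a newly dated record when an AE that began after consent gets worse. Classification is left to site habit.

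Four stronger readings might be inferred, and the documents do not support them.

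- *Such an event can never be a TEAE.* It can, by a new record or through the SAP 5.3 rules for partial and missing dates.
- *It would be visible only in the pre-treatment tables.* The SAP 7.2 tables of AEs leading to drug discontinuation and of AESIs are not restricted to TEAEs in their titles, and all AEs and SAEs are listed. Vital signs and ECGs are summarized regardless of AE onset. These displays reduce the risk of missing a signal, but they are not the primary endpoint.
- *The rule biases the trial towards safety.* It applies equally to placebo, so the effect on the difference depends on where worsening is more common, which is unknown.
- *Enough patients could be lost to matter for the DMC trigger.* Any patient count needs assumed rates. Protocol Table 3 concerns drug-related SAEs in two named categories, and a patient with another TEAE still counts in overall incidence.

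It is also fair that 18 mg is not reached before the Week 4 visit, so a run-in event would have to stay open for about four weeks to worsen at that dose. Worsening at 6 mg or 12 mg needs a shorter span, so this limits the number of cases but does not remove them.

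**Conclusion.** The concern holds in a limited form. SAP 5.2.4 is a stated rule that misclassifies a definable group: AEs starting between consent and the first randomized dose, with a known start date, unresolved at that dose, worsening or becoming serious afterwards, and kept as one record. They drop out of the primary TEAE incidence, severity and relatedness tables and, on one reading, out of the on-therapy SAE table. The total effect cannot be computed because neither document gives a rate for such events. The per-patient figures assume the planned arm sizes and no other TEAE in that patient. The arms are small enough for one misclassified patient to be visible. Observed TEAE incidence can only be lowered by the omission; the between-arm difference is understated only if worsening of this kind is more frequent on olinciguat.

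**What to change.** Before database lock and unblinding:

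- Extend the SAP 5.2.4 TEAE definition to AEs that begin before the first randomized dose and increase in CTCAE grade or become serious at or after it, within the existing window. Tabulate them at the worst post-dose grade.
- Apply the same wording to on-therapy SAEs within their own window, and say whether start means AE onset or the date of becoming serious.
- Align SAP 7.2, so that the maximum-severity rule and the pre-treatment rules do not pull these events back out of the TEAE tables.
- Check, blinded, whether the eCRF holds dated grade changes; neither document shows that it does. If not, state that such worsening is recorded as a new AE dated at the worsening.

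The cost is a small blinded data check, a programming rule and slightly higher TEAE rates. If the eCRF lacks dated grade changes, affected records may also need site queries.

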- Run-in Period:** The single-blind Run-in will begin at least 3 days after the Screening Visit and is defined as the 14 to 17 days before the first dose of double-blind study drug on Day 1. At the Run-in Visit, eligible patients will take their first single-blind (placebo) dose in the clinic, will undergo safety and pharmacodynamic (PD) assessments, and will complete patient-reported outcome (PRO) questionnaires in an eDiary (a handheld personal electronic device) that will be issued for their use. They will continue to take once-daily single-blind placebo at home and will record daily and weekly assessments in their eDiary throughout this period. Patients will be required to complete at least 10 days of daily assessments during the final 14 days of the Run-in Period to remain eligible for randomization into the Treatment Period.

Treatment Period: The double-blind Treatment Period will begin on Day 1 at Randomization (there is no Day 0) and will end after the End-of-Treatment (EOT) Visit on Day 85 (-7/+4).

Eligible patients will take their first dose of double-blind study drug in the clinic on Day 1 and will undergo safety, PRO, PK, and PD assessments at prespecified times according to the [Schedule of Events](#). Patients must remain in the clinic at least 6 hours postdose and thereafter will be allowed to leave at the Investigator's discretion. Starting on Day 2, patients will take their daily double-blind study drug dose at home, per Section [3.5.4.1](#). Also on Day 2, preferably in the afternoon, patients will receive a phone call for adverse event (AE) and concomitant medication and procedure(s) assessment. Throughout the Treatment Period, patients will continue to record daily assessments in their eDiary.

At their Week 1 (Day 8 [± 1]) and Week 4 (Day 29 [± 3]) visits, respectively, patients who meet the uptitration criteria (see Section [3.5.4.2](#)) will begin taking the applicable higher dose. At these visits, patients must again stay in the clinic at least 6 hours postdose to undergo safety, PRO, PK, and PD assessments at prespecified times according to the [Schedule of Events](#) and thereafter will be allowed to leave at the Investigator's discretion. On the day after these 3 visits, preferably in the afternoon, patients will receive a phone call for assessment of AEs and concomitant medication(s) and procedure(s).

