3.2 DISCUSSION OF STUDY DESIGN

A double-blind, placebo-controlled, randomized study design was chosen to provide comparable treatment groups and to minimize chance of selection or Investigator bias in accordance with the concepts in ICH E10, Choice of Control Groups and Related Issues in Clinical Trials (International Conference on Harmonisation of Technical Requirements for Registration of Pharmaceuticals for Human Use, 2001). Placebo was chosen as the control so that the rate of spontaneously occurring AEs can be determined and to reduce the potential for bias in the reporting of AEs.

The 2-week Run-in portion of the Screening Period will establish baseline values for daily and weekly patient-reported assessments. Treatment with single-blind placebo during this period will provide data on potential placebo response, and, in addition, will identify patients with low study drug/eDiary adherence who may benefit from retraining efforts.

The 12-week Treatment Period will compare the effects of IW-1701 with those of the placebo control. This length is sufficient to assess safety and tolerability, changes in patient-reported sickle cell-related symptoms, and changes in levels of biomarkers related to the NO-sGC-cGMP pathway.

Patients will be stratified by HU use (yes or no) to ensure equal allocation across treatment arms within stratum, which serves to control any potentially confounding influence (eg, difference in treatment response in patients taking HU).

Data Monitoring Committee (DMC) safety reviews (Section 3.7) will ensure that dosing will stop should a safety signal be detected. Patients will have a Follow-up Visit 28 (-3/+7) days after the final dose of study drug to determine if any AEs have developed and if AEs that were ongoing at the EOT Visit have resolved.

At each scheduled study visit, including the final Follow-up, women of reproductive potential will have a pregnancy test; results will be reviewed and documented prior to each in-clinic study drug administration, as applicable. Patients of both sexes will be instructed to follow the contraception requirements listed in Section 3.6.4.

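### TEAEs end 7 days after last dose: later non-serious AEs other than AESIs and VOCs reach no table named in SAP 7.2, and no later AE enters the severity or relationship tables

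*SAP*

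**What the plan says.** **Windows.** SAP 5.2.4 starts TEAEs at the first randomized dose and runs them "through 7 days after the last dose of study medication". The same section runs on-therapy SAEs "through 28 days after the final study drug dose". It gives no reason for the two lengths.

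**Endpoint.** Protocol 4.1.1 gives the primary endpoint as "Incidence, frequency, and severity of TEAEs and study drug-related TEAEs in IW-1701-treated patients compared with placebo-treated patients over the study". The protocol text sets no number of days after last dose for a TEAE.

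**Collection.** Protocol 3.8.8.7 states: "AEs will be collected and recorded from the time the patient signs the ICF at the Screening Visit through the last Follow-up Visit". SAP 7.2 agrees: "AEs are collected from date of signed informed consent form (ICF) through the last Follow-up Visit".

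**Follow-up Visit.** Protocol 3.2 places it 28 (-3/+7) days "after the final dose of study drug to determine if any AEs have developed". Protocol 3.4.3 applies the same timing to patients who stop study drug early.

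**Tables.** SAP 7.2 names 12 AE tables. Two cover pre-treatment AEs (Screening and Run-in). None is for AEs that begin after treatment. Separately, all AEs are to be listed.

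**The concern.** The primary objective is safety, and the protocol frames it as a comparison with placebo. The plan collects AEs for about four weeks off drug and states that the visit is meant to find new ones. The tables that carry the primary endpoint then stop after the first week of that period.

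Two things follow. An ordinary non-serious AE that begins in the later weeks has no incidence by arm anywhere in SAP 7.2, only a line in a listing. And severity and drug relatedness, which are named components of the primary endpoint, are tabulated only for TEAEs. A severe, drug-related SAE on day 10 off drug would therefore be counted in the SAE table but would be absent from both the severity and the relationship table. The separate listings of severe TEAEs and of drug-related TEAEs would leave it out as well.

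**Working it through.** **Inputs**
- TEAE window: last dose + 7 days (SAP 5.2.4).
- On-therapy SAE window: last dose + 28 days (SAP 5.2.4).
- End of treatment: Day 85; Follow-up Visit: Day 113 (-3/+7) (Protocol 3.1).
- *F*, the days from last dose to the Follow-up Visit: 28, with limits 25 and 35 (Protocol 3.2).

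**Step 1: the plan's own dates.** 85 + 28 = 113, which agrees with the schedule. The limits are 113 - 3 - 85 = 25 and 113 + 7 - 85 = 35 days.

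**Step 2: follow-up days outside the TEAE window.** Share = (*F* - 7) / *F*.

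| *F* | Days outside | Share of follow-up | Share of Day 1 to Follow-up |
|---|---|---|---|
| 25 | 18 | 18/25 = 72% | 18/110 = 16.4% |
| 28 | 21 | 21/28 = 75% | 21/113 = 18.6% |
| 35 | 28 | 28/35 = 80% | 28/120 = 23.3% |

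With a last dose on Day 85, TEAEs end on Day 92 (85 + 7) and on-therapy SAEs on Day 113 (85 + 28). If the visit is late, SAEs on days 29 to 35 off drug also fall outside the on-therapy SAE table.

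**Step 3: where an AE starting after day 7 off drug can appear (SAP 7.2).**

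| Tables | Content | Takes such an AE? |
|---|---|---|
| 1, 2, 3, 4, 10 | TEAEs: overall, SOC/PT, severity, relationship, region | No, by definition |
| 5 | On-therapy SAEs by PT | SAEs to day 28 only |
| 6 | AEs leading to drug discontinuation | Not in practice, as drug has already stopped |
| 7, 8 | Pre-treatment AEs | No |
| 9 | AESIs by PT | Possibly; no window stated |
| 11, 12 | VOCs by PT; by location and outcome | Possibly; no window stated |

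A non-serious AE that is neither an AESI nor a VOC has no table. Tables 5, 9, 11 and 12 can take some late events, but none of them is described as giving CTCAE grade or relationship. Those two breakdowns are in tables 3 and 4, which are limited to TEAEs.

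**Step 4: can days be turned into events?** Let *q* be the share of follow-up AEs that reach tables 5, 9, 11 or 12. Assume a constant AE rate after last dose. The untabulated share of events is then (*F* - 7)/*F* × (1 - *q*). At *F* = 28:
- *q* = 0: 75%
- *q* = 0.2: 60%
- *q* = 1/3: 50%
- *q* = 0.5: 37.5%

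The share exceeds one half only if *q* is below 1 - 0.5*F*/(*F* - 7). That limit is 0.31 at *F* = 25, 0.33 at *F* = 28 and 0.38 at *F* = 35. The documents give neither *q* nor an AE rate.

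**The case against.** The case for leaving the plan alone is substantial, and most of it stands against stronger readings of this point.

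- **A reader might infer that most follow-up AEs are in no table.** The documents do not support that. The 72% to 80% is a share of days. SAEs to day 28 have table 5, and the AESI and VOC tables carry no stated TEAE limit. Protocol 3.8.8.6 expects crises in this population, so *q* could be large.
- **A reader might infer that the SAP contradicts the protocol.** It does not. The protocol's phrase about the whole study qualifies TEAEs, a term for which the protocol gives no window. The SAP fills a gap, and Protocol 5.1 leaves data-handling detail to it.
- **A reader might infer that SAE and TEAE counts cannot be reconciled.** The two windows are explicit and separately named, and SAEs and TEAEs are listed separately. The SAEs that fall between the windows can be identified, although no table shows them as such.
- **A reader might infer that effects of stopping the drug are never compared between arms.** SAP Table 9 summarises vital signs at the Follow-up Visit. SAP Table 7 tabulates Grade 3 or higher laboratory values through the last measurement. AESIs cover hypotension, tachycardia, bleeding, pulmonary edema and bone events. No withdrawal effect is documented.

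A 7-day window can also be a legitimate choice, and nothing in the documents shows it to be too short. Finally, the index of tables and the table shells are not available, so absence of a table is checked only against SAP 7.2.

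What this leaves untouched is the narrower gap. Vital-sign, laboratory and AESI summaries do not replace a general AE table, and a listing gives no incidence by arm. The limit on the severity and relationship tables holds whatever *q* is.

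**Conclusion.** The point holds in limited form, as a cheap improvement rather than an error. AEs are collected for 25 to 35 days after last dose. Non-serious AEs that start after day 7, other than AESIs and VOCs, are listed but summarised in no table that SAP 7.2 names. No AE starting after day 7 contributes to the severity or relationship tables.

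The size is 21 of 28 follow-up days (75%; range 72% to 80%), or about 19% of the time from Day 1 to the Follow-up Visit. The number and share of events affected are unknown. No data are lost, and the TEAE results within their own window are unaffected.

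The conclusion rests on two assumptions: that SAP 7.2 names all the AE summary tables, and that the AESI and VOC tables may extend into follow-up because their titles state no window. If those tables were also cut at 7 days, the gap would widen to include non-serious AESIs and VOCs.

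**What to change.** - Keep the 7-day TEAE tables as they are.
- Add one table, by arm, of AEs starting from day 8 after last dose through the Follow-up Visit, by SOC and PT, with severity and relationship to study drug. Do not cap it at day 28. A cap would leave up to 7 days (29 to 35) uncovered when the visit is late, whereas running to the visit brings the uncovered days from 21 of 28 to 0.
- Add a row to the overall AE summary for all AEs starting after the first randomized dose, through the Follow-up Visit.
- State in SAP 7.2 which window applies to the AESI table and the two VOC tables.

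**Cost:** SAP wording, one more table and one more row. The data are already collected, so no protocol or eCRF change is needed. The counts will be small: under Amendment 4 and later about 48 × 3/4 = 36 patients receive 18 mg and 48 × 1/4 = 12 receive placebo. The new table should therefore be descriptive, as the other safety tables are.
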